7.4.3 Other Efficacy Endpoints

- AUC of subject's NRS will be examined over various time periods: $AUC_{0 \text{ to } 6h}$, $AUC_{0 \text{ to } 12h}$, $AUC_{0 \text{ to } 24h}$, $AUC_{0 \text{ to } 120h}$, $AUC_{0 \text{ to } w1}$ (walking), $AUC_{0 \text{ to } w2}$, $AUC_{0 \text{ to } w2}$ (walking), $AUC_{12 \text{ to } 24h}$, $AUC_{24 \text{ to } 48h}$, $AUC_{24 \text{ to } 72h}$, $AUC_{24 \text{ to } 96h}$, $AUC_{96 \text{ to } 120h}$, $AUC_{96h \text{ to } w1}$, $AUC_{24h \text{ to } w1}$ (walking), $AUC_{96h \text{ to } w2}$, $AUC_{96h \text{ to } w2}$ (walking).
- Time-specific ("milestone") mean pain intensity NRS at 6, 12, 24, 28, 72, 96, 120, 144, and 168 hours
- Time-specific ("milestone") mean pain intensity NRS by site at 6, 12, 24, 28, 72, 96, 120, 144, and 168 hours
- OC over following time periods: $OC_{24 \text{ to } 48h}$, $OC_{24 \text{ to } 72h}$, $OC_{24 \text{ to } 96h}$.
- OF over following time periods: $OF_{24 \text{ to } 96h}$, $OF_{96h \text{ to } w1}$, $OF_{96h \text{ to } w2}$.
- Time to first use of rescue medication ($TTFR_{\text{after } T0}$) and first use after 24 hours ($TTFR_{\text{after } T24h}$). For the analysis of time to use of rescue medication, only OPIOID rescue medication will be considered,
- Analgesic consumption (AC) from T96h to W1 ($AC_{96h \text{ to } W1}$) and $AC_{96h \text{ to } W2}$.
- Patient global evaluation (PGE) comparing the percentage of subjects reporting (poor or fair) versus (good or excellent) responses and the percentage reporting each category of response at W1, W2 and W4.
- Investigator's global evaluation (IGE) comparing the percentage of those reporting (poor or fair) versus (good or excellent) responses and the percentage reporting each category at W1, W2 and W4.
- Number and percentage of subjects who drop out due to an AE or lack of efficacy (LOE) during the inpatient period: $LOE_{24 \text{ to } 96h}$, $LOE_{0 \text{ to } 96h}$.

- Health care utilization after discharge from the inpatient unit: HCU_{96h to W2} and HCU_{96h to W4}. (Not included in this SAP)

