
Efficacy Parameter Assessment Times:
	
1. NRS scores will be assessed as follows:
 
 
• During the inpatient stay, at T0.5, 1, 2, 4, 6, 8, 12, 16, 20, 24, and every 4 hours (if awake at time of assessment and if no rescue opioid had been administered in the past 4 hours) until discharge from the inpatient unit.
 
• Pain scores may be skipped between the hours of midnight and 6 a.m., but the subject may not miss two consecutive assessments.
 
• An additional NRS assessment must be obtained 4 hours (<math>\pm 15</math> min) after every rescue dose even if this time point occurs between midnight and 6 a.m. The T12, T24, T48, T72 and T96h assessments must be completed even if the subject is asleep at these times.
 
• During the inpatient stay, starting on postoperative day 1 (after T24): each morning on arising at approximately 0800h (<math>\pm 2</math>h) and each evening prior to bedtime at approximately 2000h (<math>\pm 2</math>h) document the NRS score with partial (e.g., transfers to or from bed or wheelchair) or full ambulation of approximately 10 yards (must document time of assessment). Actual assessment times must be documented.
 
• During the outpatient period, twice daily at approximately 0800h (<math>\pm 3</math>h) and 2000h (<math>\pm 3</math>h) document the NRS score at rest and with ambulation of approximately 10 yards. Note that the actual time of these assessments must be documented in the diary.
 
 
2. Total opioid consumption (OC) and daily opioid (rescue medication) consumption in MEDs will be recorded during the inpatient period.

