7 EFFICACY EVALUATION

7.1 Handling of Dropouts or Missing Data

All efforts will be made to minimize missing data. These efforts will include the following:

- Subjects are required to consent to continuous data collection even after discontinuation of study medication;
- Data collection will continue after subjects take rescue medication.

With the procedures above, it is expected that missing data will be minimal. Missing at random is expected to be a reasonable assumption for this dose-escalation study.

For the endpoints of NRS (at rest and/or after ambulation) in this study, NRS values will be imputed in the following manner:

First, when rescue medication is used, any NRS measured at rest within the next 4 hours is considered invalid. Therefore, the last NRS prior to the use of any rescue medication will be used to impute subsequent NRS at rest scores for the subsequent protocol-specified time points for measurement of pain intensity through 4-hours after the time of the dosing of the rescue medication. Note: if a pre-rescue NRS assessment occurs at the same time as a scheduled assessment, the schedule NRS will be assumed to happen first, and then the pre-rescue NRS will be assumed to occur. If an NRS assessment occurs at the same time as the time of taking a rescue medication, the NRS will be assumed to be a Pre-rescue medication result. If the NRS time is the same as 4 hours after taking the rescue medication (end of imputation period), then NRS will be considered as occurring before the 4 hours assessment and will be imputed. For example, if a rescue dose is taken at 1pm, all protocol-scheduled NRS will be imputed with the appropriate NRS value up to and including through 5pm. If multiple doses of rescue medication are taken within a 4-hour period, the pre-rescue NRS for the first rescue use will be carried forward continuously until 4 hours past the last use of rescue falling within the continuous window. For example, if rescue is used at Hour 2.3 and Hour 5.1, the pre-rescue NRS at Hour 2.3 will be carried forward till Hour 9.1 (5.1 +4). NRS scores taken after ambulation will be based on reported values and the pre-rescue 4-hour imputation rule will not be used. The scores after ambulation are collected every 12 hours and no ambulation NRS score is collected prior to taking rescue medication.

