7.5.2 AUC Outcomes

All AUC calculations will be done using the standard trapezoidal rule

$$AUC = \sum_{i=0}^x \left(\frac{NPRS_i + NPRS_{i+1}}{2} \right) * (T_{i+1} - T_i)$$

Where: NRS_i = NRS at rest at time i , and $(T_{i+1} - T_i)$ is the Time difference in hours between time i and time $i+1$.

Missing NRS will be handled as discussed in Section 7.1. A similar calculation of AUC and handling of missing data will be performed for the NRS scores with ambulation and are designated as AUC_{0-x (walking)}. Both pre-rescue and post-rescue scores will be used in the AUC calculations.

AUC values will be analyzed using a 1-factor (treatment) analysis of variance (ANOVA) model with treatment as the main effect. In addition to the comparisons between each CA-008 group and the placebo group, the test for a linear trend across dose groups will be carried out using the contrast of -1.75, -1.05, 0.35 and 2.45 for placebo, 0.7 mg, 2.1 mg and 4.2 mg group, respectively.

The AUC analyses will be presented in a summary table with standard summary statistics for each treatment group as well as active vs. placebo mean differences, standard errors, confidence intervals and comparison p-values as appropriate. Comparisons of individual treated group response may be presented for certain secondary AUC endpoints.

The individual NRS and the computed AUC variables will be listed for all individual subjects.

The primary analysis of the primary endpoint ((AUC_{0 to 96h}) and secondary AUC endpoints will be based on the mITT population. In addition, the primary and other AUC efficacy endpoints may be analyzed using inpatient CP and/or CP population as appropriate for sensitivity.

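### Two walking-pain AUCs are labelled as starting at time 0, but no walking score is scheduled until after T24h

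*SAP*

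**What the plan says.** SAP 7.4.3 (Other Efficacy Endpoints) states that AUC of the "NRS will be examined over various time periods". Its list includes AUC0 to W1 (walking), AUC0 to W2 (walking), AUC24h to W1 (walking) and AUC96h to W2 (walking). The protocol synopsis, under Other Endpoints, has the same four. Protocol 12.6.1.3 has AUC0 to W1 (walking) but not AUC0 to W2 (walking).

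On collection, the synopsis says: "During the inpatient stay, starting on postoperative day 1 (after T24): each morning on arising at approximately 0800h", with a second score each evening at about 2000h, both within 2 hours. Protocol 9.1.4 repeats this. SAP 7.1 adds: "The scores after ambulation are collected every 12 hours and no ambulation NRS score is collected prior to taking rescue medication". SAP 7.5.1 describes walking scores only for the outpatient diary.

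On calculation, SAP 7.5.2 says: "A similar calculation of AUC and handling of missing data will be performed for the NRS scores with ambulation", and it gives the results a general walking-AUC label that starts at 0. SAP 7.2 requires actual assessment times.

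**The concern.** An AUC named from time 0 should rest on scores that begin at or near time 0. For walking pain, the schedule contains none before T24h.

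A reader of the results tables would take AUC0 to W1 (walking) as evidence on pain with movement from surgery onward. The missing stretch also matters for interpretation. Protocol 7.1.4 expects background analgesia to carry the first 24 hours and the drug's own effect to follow, so the part never measured is where the drug is expected to do least. Under SAP 7.5.2 these endpoints receive ANOVA comparisons with p-values.

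There is a second, smaller cost. Walking assessments follow the clock rather than T0, so the point at which a subject's area begins depends on the time of day of surgery.

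**Working it through.** **The plan's own figure.** The documents give no figure for walking AUCs. The only related calculation is the sample size for the primary endpoint, AUC0 to 96h at rest (Protocol 15.2, SAP 2.2.4): difference 100, SD 130, two-sided 0.05, 90% power. n per arm = 2 × (1.960 + 1.282)² × 130² / 100² = 35.5, rounded up to 36. Power at 36 per arm is 90.4% by the normal formula; by noncentral t it is 89.6% (70 df) or 90.0% (140 df, four-arm ANOVA). The figure is reproduced, and this point does not touch it.

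**Step 1: does any rule supply a walking score between T0 and T24h?**

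| Rule (SAP) | Effect on walking scores, T0 to T24h |
|---|---|
| Pre-rescue score carried for 4 hours (7.1) | Not used for walking scores |
| Intermittent missing scores (7.1) | Not imputed; these hours are in any case unscheduled rather than missing |
| Worst score carried forward after dropout or prohibited medication (7.1) | Carries forward only, and needs an earlier walking score |
| Sensitivity: last score carried forward (7.1) | Same |
| Sensitivity: group median after dropout (7.1) | No walking scores exist in this stretch from which to take a median |

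None does.

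**Step 2: where does the sum start?** Assume T0 falls between 07:00 and 17:00; the documents give no surgery times. Take the first 0800h or 2000h slot after T24h.

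| T0 (clock) | Nominal first walking score |
|---|---|
| 07:00 | T25h |
| 08:00 | T36h |
| 12:00 | T32h |
| 17:00 | T27h |

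The nominal range is T25 to T36h. With the 2-hour windows it is T24 to T38h.

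**Step 3: unobserved share of the named interval.** The documents do not give W1 and W2 in hours. Counting 7 and 14 days gives 168 and 336 h. Counting D8 and D15 from D0 gives 192 and 360 h.

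| Interval | 24 h unobserved | 38 h unobserved |
|---|---|---|
| W1 = 168 h | 24/168 = 14.3% | 38/168 = 22.6% |
| W1 = 192 h | 24/192 = 12.5% | 38/192 = 19.8% |
| W2 = 336 h | 24/336 = 7.1% | 38/336 = 11.3% |
| W2 = 360 h | 24/360 = 6.7% | 38/360 = 10.6% |

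**Step 4: scale in NRS-hours.** No walking pain level is given, so take 3, 5 and 7 as assumptions.

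- Area left out, compared with carrying the first score back to T0: 24 h × 3, 5, 7 = 72, 120, 168; 36 h × 3, 5, 7 = 108, 180, 252.
- Difference between two subjects with the same constant pain who start 14 h apart (T24 and T38h): 14 × 3, 5, 7 = 42, 70, 98.

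For orientation only, the planned treatment difference on the rest AUC0 to 96h is 100.

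**Step 5: duplication.** If both calculations start at the first walking score after T24h, AUC0 to W1 (walking) and AUC24h to W1 (walking) sum the same trapezoids. AUC96h to W2 (walking) is unaffected.

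**The case against.** Four points can be made for the plan.

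- **A value can be computed.** A reader might infer that these endpoints cannot be calculated at all. The documents do not support that: AUC is calculated from non-missing values at actual times, so a program will return a number. The rest AUCs named from 0 also begin at their first score, at T0.5h. This stands, and it makes the defect one of labelling and redundancy. But a half-hour gap is trivial and a gap of 24 h or more is not.
- **The comparison between arms is not shown to be biased.** A reader might infer that the treatment difference is wrong, or wrong by the NRS-hours in Step 4. That does not follow. The first day is unmeasured by design in every arm, and randomisation should balance the time of surgery. The figures in Step 4 are per-subject areas at assumed pain levels, not errors in an effect estimate. This stands in full.
- **The 24h endpoints have the same weakness.** No walking score is scheduled at T24h itself, so AUC24h to W1 (walking) also starts at a subject-dependent time. This stands, and deleting the endpoints from 0 would not cure it.
- **A site might score on the morning after surgery, before T24h.** With T0 at 15:00, 08:00 the next day is T17h. The protocol's wording rules this out, and even then no score would lie near T0.

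The consequence is also limited. The primary endpoint and the key secondary AUC use rest scores, and the walking AUCs are tested without multiplicity adjustment.

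**Conclusion.** The point holds as a minor one. Two walking AUCs are named for an interval whose first 24 h or more is never measured: at least 12.5% to 14.3% of the W1 interval and 6.7% to 7.1% of the W2 interval, depending on how those weeks are counted in hours. One of the two essentially repeats another listed endpoint. The results would overstate first-day coverage and carry some between-subject variation that comes from the time of surgery.

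That no walking score is scheduled before T24h rests on the documents alone. The T24 to T38h range rests on the assumed surgery times, the percentages on the assumed lengths of W1 and W2, and the NRS-hour figures on assumed walking scores. Nothing here affects the primary endpoint, the key secondary endpoints, the sample size or power.

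**What to change.** Before database lock:

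1. Delete AUC0 to W1 (walking) and AUC0 to W2 (walking).
2. Keep AUC24h to W1 (walking) and add AUC24h to W2 (walking).
3. Define both as starting at the first walking score after T24h, and divide the area by the observed duration. The resulting time-weighted average on the 0 to 10 scale keeps the varying start from driving the value.
4. Align the protocol synopsis, Protocol 12.6.1.3 and SAP 7.4.3, which already disagree on AUC0 to W2 (walking), and change the general walking-AUC label in SAP 7.5.2.
5. Use the new names for the rows within Tables 14.2.1.3 to 14.2.1.5. Their titles name no specific period and can stay.

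The cost is small wording edits to the SAP and to the protocol's endpoint lists. No new data are needed and power does not change.

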7.5 Analysis Methods

7.5.1 NRS Measurements

The NRS is an 11-point scale with anchors 0 (no pain) and 10 (worst possible pain). Subjects should be at rest for at least 10 minutes prior to completing NRS resting assessments and have ambulated approximately 10 yards within 15 minutes prior to completing NRS ambulation assessments.

During the inpatient stay, NRS pain assessments will be collected at Hours 0.5, 1, 2, 4, 6, 8, 12, 16, 20, 24, and every 4 hours (if awake at time of assessment and if no rescue opioid had been administered in the past 4 hours) until discharge from the inpatient unit. Pain scores may be skipped between the hours of midnight and 6 a.m., but the subject may not miss two consecutive assessments. A pre-rescue NRS will be collected prior to each use of rescue. An additional NRS assessment must be obtained 4 hours (± 15 min) after every rescue dose even if this time point occurs between midnight and 6 a.m. Hours 12, 24, 48, 72 and 96 assessments must be completed even if the subject is asleep at these times. Note, a 5-minute window is allowed for the collection of each assessment in the first 4 hours after the end of surgery, after which will be a 15-minute window allowed.

During the outpatient period (up to Day 15), NRS will be assessed twice daily at approximately 08:00 (± 3 h) and 20:00 (± 3 h) at rest and with ambulation of approximately 10 yards. The results and the actual time of assessments will be documented in subjects' diary. In addition, the subject will be asked to complete a pre-rescue NRS each time they take rescue.

Mean NRS scores over time (in-patient and diary) will be summarized and graphed over time by treatment. NRS over time by each subject will also be displayed graphically.

7.5.2 AUC Outcomes

All AUC calculations will be done using the standard trapezoidal rule

$$AUC = \sum_{i=0}^x \left(\frac{NPRS_i + NPRS_{i+1}}{2} \right) * (T_{i+1} - T_i)$$

Where: NRS_i = NRS at rest at time i , and $(T_{i+1} - T_i)$ is the Time difference in hours between time i and time $i+1$.

Missing NRS will be handled as discussed in Section 7.1. A similar calculation of AUC and handling of missing data will be performed for the NRS scores with ambulation and are designated as AUC_{0-x (walking)}. Both pre-rescue and post-rescue scores will be used in the AUC calculations.

AUC values will be analyzed using a 1-factor (treatment) analysis of variance (ANOVA) model with treatment as the main effect. In addition to the comparisons between each CA-008 group and the placebo group, the test for a linear trend across dose groups will be carried out using the contrast of -1.75, -1.05, 0.35 and 2.45 for placebo, 0.7 mg, 2.1 mg and 4.2 mg group, respectively.

The AUC analyses will be presented in a summary table with standard summary statistics for each treatment group as well as active vs. placebo mean differences, standard errors, confidence intervals and comparison p-values as appropriate. Comparisons of individual treated group response may be presented for certain secondary AUC endpoints.

The individual NRS and the computed AUC variables will be listed for all individual subjects.

The primary analysis of the primary endpoint ((AUC_{0 to 96h}) and secondary AUC endpoints will be based on the mITT population. In addition, the primary and other AUC efficacy endpoints may be analyzed using inpatient CP and/or CP population as appropriate for sensitivity.

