### 15.6.1. Primary Efficacy Analysis

The primary efficacy analysis of the primary endpoint ( $AUC_{0 \text{ to } 96h}$ ) will be conducted using an analysis of variance (ANOVA) model with treatment group (four levels) as the main effect. The primary analysis will compare the 4.2 mg CA-008 group to the placebo group using a two-sided test at the  $\alpha=0.05$  level of significance.

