2.2.3 Treatment Group Assignments or Randomization

The study will be conducted in a randomized, double-blinded and placebo-controlled manner. The study includes 4 treatment groups (3 active and 1 placebo group). Subjects who meet the enrollment criteria will be randomly allocated in a 1:1:1:1 ratio to receive either active drug or placebo. Randomization will be accomplished manually on the day of surgery.

Subjects who have provided written informed consent will be assigned a unique number in the screening process. This number will be used to identify the subject throughout the study. Prior to randomization, subjects must meet all inclusion and not meet any exclusion criteria (as described in Sections 10.1 and 10.2). Once any subject number or randomization number is assigned, it cannot be reassigned to any other subject.

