2.2.4 Sample Size Determination

In the previously completed Phase 1 ascending dose safety study in bunionectomy (CA-008 vs. placebo), the mean difference between CA-008 (all dose groups combined) and placebo for the area under the curve (AUC) from 24 to 96 hours was -120. The standard deviation (SD) estimates for the six treatment arms in this study ranged from 70 to 190 with a median SD of 108. For the primary endpoint (AUC₀ to 96h), the true treatment difference between the 4.2 mg CA-008 group and the placebo group is assumed to be equal to -100 and the assumed true SD is equal to 130. For these assumptions, and based on the use of a two-sided, two-sample comparison of means at the alpha=0.05 level of significance, a sample size of 36 subjects per arm will provide 90% power. Thus, the target sample size is 144 subjects.

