Table 14.2.2.5.1	mITT Population	Summary of NRS at Rest and with Walking by Time Point (WOCF)
Table 14.2.2.5.2	mITT Population	Summary of NRS at Rest and with Walking by Time Point and by Site (WOCF)

Table 14.2.2.6	mITT Population	Summary of NRS at Rest and with Walking by Time Point (LOCF)
Table 14.2.2.7.1	mITT Population	Summary of NRS at Rest and with Walking by Time Point (Observed Data, No Imputation for Drop Out)
Table 14.2.2.7.2	mITT Population	Summary of NRS at Rest and with Walking by Time Point and by Site (Observed Data, No Imputation for Drop Out)
Table 14.2.3	mITT Population	Logistic Analysis of Proportion of Subjects who are Opioid Free Outcome (Key Secondary and Exploratory Analyses)
Table 14.2.4.1.1	mITT Population	ANOVA Analysis of Opioid Consumption (in Morphine equivalents) (Key Secondary and Exploratory Analyses)
Table 14.2.4.1.2	mITT Population	ANOVA Analysis of Opioid Consumption by Site (in Morphine equivalents) (Key Secondary and Exploratory Analyses)
Table 14.2.4.2.1	mITT Population – Subjects Who Took Any Opioid Medication	ANOVA Analysis Mean Daily Opioid Consumption (in Morphine Equivalents)
Table 14.2.4.2.2	mITT Population – Subjects Who Took Any Opioid Medication	ANOVA Analysis Mean Daily Opioid Consumption by Site (in Morphine Equivalents)
Table 14.2.5.1	Safety Population	Kaplan-Meier Analysis of Time to First Use of Opioid Rescue Medication
Table 14.2.5.2	Safety Population – Subjects Who Took First Opioid Rescue Medication Prior to 60 Minutes Post-Dose	Kaplan-Meier Analysis of Time to Second Use of Opioid Rescue Medication
Table 14.2.6	mITT Population	CMH and Fishers Analysis of Patient Global Evaluation (PGE)
Table 14.2.7	mITT Population	CMH and Fishers Analysis of Investigator Global Evaluation (IGE)
Table 14.2.8	mITT Population	Fishers Analysis of Proportion of Drop Out During the Inpatient Period
Table 14.2.9.1	Safety Population	Fishers Analysis of Percent of Subjects using Rescue Medication Over Time
Table 14.2.9.2	Safety Population	Summary of Percent of Subjects Using Rescue Medication by Day
Table 14.3.1.1	Safety Population	Overall Summary of Treatment-Emergent Adverse Events (TEAEs)
Table 14.3.1.2	Safety Population	Summary of TEAEs by System Organ Class and Preferred Term

Table 14.3.1.3	Safety Population	Summary of Treatment Related TEAEs by System Organ Class and Preferred Term
Table 14.3.1.4	Safety Population	Summary of SAEs by System Organ Class and Preferred Term

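### The primary and key secondary models leave site out of a trial run at about three sites; adding it is a cheap efficiency gain, not the repair of an error

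*SAP*

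**What the plan says.** For the primary endpoint, Protocol 15.6.1 specifies an "analysis of variance (ANOVA) model with treatment group (four levels) as the main effect". SAP 7.5.2 repeats this for every AUC endpoint: "AUC values will be analyzed using a 1-factor (treatment) analysis of variance (ANOVA) model with treatment as the main effect". SAP 7.5.4 applies an ANOVA with treatment arm alone to opioid consumption, and SAP 7.5.3 a logistic regression with treatment alone to the opioid-free outcome.

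The Protocol synopsis plans about three US sites. Site appears in the planned output: SAP 7.4.3 lists "mean pain intensity NRS by site at 6, 12, 24, 28, 72, 96, 120, 144, and 168 hours", and SAP 14.1.1 lists by-site tables of NRS by time point and by-site ANOVA tables of opioid consumption. No by-site or site-adjusted analysis of the primary AUC is listed. The sensitivity analyses in SAP 7.1, 7.5.2 and 14.1.1 vary only the imputation method and the population.

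On allocation, SAP 2.2.3 says subjects are "randomly allocated in a 1:1:1:1 ratio to receive either active drug or placebo" and "Randomization will be accomplished manually on the day of surgery". Neither document says whether the list is stratified or blocked by site.

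**The concern.** In a one-factor model, any difference in mean pain between sites stays in the error term and widens the interval for 4.2 mg versus placebo. Chance imbalance of sites between arms is not corrected either. Some pain-relevant steps are left to local judgement: sedation and additional anesthetics, block volume up to a maximum, and adjustment of the ketorolac dose. A site effect on a 96-hour pain AUC is therefore plausible, though not shown.

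The primary test also opens the key secondary hierarchy (Protocol 15.6.2, SAP 7.3), so power gained or lost there carries down to the opioid endpoints. Site is recorded before treatment, and each site is supplied for all arms (Protocol 11.3). It is thus a legitimate covariate whether or not allocation was stratified on it.

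**Working it through.** **Inputs from the documents.** Difference 100 and SD 130 on AUC0-96h, 36 per arm, four arms, 90% power, and a "two-sided, two-sample comparison of means at the alpha=0.05 level of significance" (Protocol 15.2, SAP 2.2.4).

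**Assumed inputs.** ρ, the share of within-arm AUC0-96h variance lying between sites, is taken from 0 to 20% because the documents give none. Also assumed: three equal sites, the same treatment effect at each, and no dropout.

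**1. Reproduce the stated power.** SE = 130 × √(2/36) = 30.64, and the noncentrality is 100/30.64 = 3.264. Power from the noncentral t is 89.6% for a two-sample test (70 df) and 90.0% for the four-arm ANOVA with pooled error (144 − 4 = 140 df). The plan's 90% is confirmed. The 95% CI half-width is 1.977 × 30.64 = 60.6.

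**2. Add site (two extra parameters, 138 df), sites balanced across arms.** Residual SD = 130 × √(1 − ρ). Equivalent sample size per arm under the one-factor model = 36/(1 − ρ).

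| ρ (assumed) | Residual SD | Power | CI half-width | Equivalent n per arm |
|---|---|---|---|---|
| 0 | 130.0 | 90.0% | 60.6 | 36 |
| 5% | 126.7 | 91.4% | 59.1 | 37.9 |
| 10% | 123.3 | 92.7% | 57.5 | 40.0 |
| 20% | 116.3 | 95.2% | 54.2 | 45.0 |

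**3. Same model under simple randomization.** Chance imbalance inflates the variance of the adjusted difference by about 141/139 = 1.014. Power becomes 89.6%, 91.0%, 92.4% and 94.9% at ρ = 0, 5%, 10% and 20%. The one-factor model stays at 90.0% throughout. Break-even is where (1 − ρ) × 141/139 = 1, so ρ is about 1.4%. Simulation with 6,000 trials per setting agrees with these figures to within about half a point.

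**4. What ρ means on the pain scale.** With three equally spaced site means, the gap between the highest and lowest is 2 × 130 × √(1.5ρ). Dividing by 96 h gives the average NRS gap: about 0.4 points at 1.4%, 0.7 at 5%, 1.0 at 10% and 1.5 at 20%.

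**5. Two conditional cases.**
- If 130 is really a within-site SD, the total SD is 130/√(1 − ρ) = 133.4, 137.0 or 145.3 at ρ = 5%, 10% or 20%. The one-factor model then has power 88.5%, 86.8% or 82.6%, and the site-adjusted model holds 90.0%.
- If allocation is in fact balanced by site, leaving site out overstates the standard error by about √(1 + (144/140) × ρ/(1 − ρ)) = 1.027, 1.056 or 1.121. The real two-sided alpha is then about 0.044, 0.039 or 0.028: conservative, never inflated.

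**The case against.** The strongest reply is that nothing is wrong. Protocol and SAP agree on the model, the test holds its level, and the planned power is delivered by exactly this analysis. All of that stands. A reader might infer from the missing site term that the primary analysis is invalid, biased or underpowered. The documents do not support this: under simple randomization the one-factor comparison is valid, and 90% reproduces on the plan's own assumptions.

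A reader might also infer that precision is certainly being lost and that recovering it is free. Neither follows. The benefit depends wholly on a between-site variance that is not given, and at 5% it is worth about two subjects per arm. The cost is small but not zero (working, step 3).

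Nor do local delivery or the by-site tables establish a site effect. The protocol fixes the block agent, its maximum volume and timing, the 14 mL of study treatment in set aliquots, and the rescue drug with its pain threshold. The by-site output covers NRS and opioid consumption, not the primary AUC, and planning a table is not evidence of a difference.

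A last objection concerns the remedy. Adjusting the AUC and OC models while saying nothing of OF0-96h, the first key secondary endpoint, would leave the hierarchy mixed. An unspecified pooling rule would also put an analyst's choice into the primary model. Both points are right and are met in the fix.

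**Conclusion.** The point holds as an efficiency improvement. On the assumed range of 5% to 20% of variance between sites, a site term adds about 1.4 to 5.2 points of power with balanced sites, or 1.0 to 4.9 under simple randomization. It narrows the CI half-width by 1.5 to 6.4 units out of 60.6. The worst case is a loss of about 0.4 points. The trade favours adjustment unless site explains less than about 1.4% of the variance. These figures rest on three equal sites, a common treatment effect and no dropout; unequal sites would change them somewhat. The case for acting is that the change is nearly free, not that the present analysis fails.

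**What to change.** Before unblinding, amend SAP 7.5.2 and 7.5.4:

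- Fit treatment and site as fixed factors in the ANOVA for AUC0-96h, OC0-96h and AUC0-W1.
- Set the pooling rule for small sites in advance, for example merging any site that lacks at least one mITT subject in each arm with the next smallest site.
- State in SAP 7.5.3 whether the OF0-96h logistic model also includes site, so that the hierarchy is consistent. Adjustment changes what the odds ratio measures, so this should be a stated choice.
- Keep the one-factor model as a pre-specified sensitivity analysis.
- State in SAP 2.2.3 whether the manual randomization is balanced by site.
- Reconcile Protocol 15.6.2, which refers back to an ANCOVA, with 15.6.1, which describes an ANOVA without covariates. Record the model change in SAP 12.

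The cost is a few lines of text, one model term and 2 degrees of freedom, with no new data. Timing matters because SAP 1 and 10 require analyses added after database lock to be labelled post hoc.
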